3.3.5. Sample size

In order to achieve statistical power of at least 95% at 5% significance level of two-sided hypotheses for the evaluation of 10% standardized mean differences of fat and protein composition of HM, as well as growth markers (weight, height), and health status (number of gastrointestinal and respiratory diseases) of preterm infants, a total of 75 mother-infant dyads (25 per Group of Study II) will be enrolled.

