3.3.1. Study design

The proposed study is an observational, parallel group, non-randomized study in lactating mothers. It will be carried out at the University and Polytechnic Hospital La Fe (HULAFE), beginning at Month 21. Previously, the study protocol will be approved by the Ethics Committee for Biomedical Research of the Health Research Institute La Fe (Valencia, Spain) and the study participants will sign a relevant consent form. All procedures regarding volunteers' recruitment and participation, data security and handling will be in absolute accordance with the principles set under WP 9, concerning Ethical Requirements, and more specifically stated on Tasks 7.1 and 7.2 and D 7.2.

To address the objectives mentioned above, three mother-infant groups will be examined. In specific:

- Group A will consist of 25 pre-term infants fed with OMM (PT-OMM) and their mothers.
- Group B will consist of 25 pre-term infants fed with pasteurized DHM (PT-DHM), in range of complete enteral nutrition (150 mL/kg/day), and their mothers.
- Group C will consist of 25 full term infants receiving OMM (FT-OMM) and their mothers.

The study will be divided into two phases:

- A baseline phase, referring to the period between the time of delivery and the time preterm infants receive complete enteral nutrition (CEN) and full term infants recover of birth weight (RBW). During this period, all infants and their mothers will be evaluated, as described in the next section.
- 2. **An observational phase**, lasting six months and referring to the period that infants are fed with HMand/or formulas orsolid foods. During this period, assessments, as described below,

[figure not shown]

will be arranged for all mother-infants dyad and the donors providing the DHM in the hospital or the participants' home.

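### Study II claims at least 95% power for a 10% standardized mean difference with 25 dyads per group; as written, the power is about 6%

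*Protocol*

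**What the plan says.** The protocol's section 3.3.5 gives the whole sample-size argument for Study II in one sentence. It promises "statistical power of at least 95% at 5% significance level of two-sided hypotheses for the evaluation of 10% standardized mean differences", applies this to the fat and protein content of human milk, extends it to further outcomes, "as well as growth markers (weight, height), and health status (number of gastrointestinal and respiratory diseases) of preterm infants", and concludes that "a total of 75 mother-infant dyads (25 per Group of Study II) will be enrolled".

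Section 3.3.1 confirms the group size. For example, "Group A will consist of 25 pre-term infants fed with OMM (PT-OMM) and their mothers" and "Group C will consist of 25 full term infants receiving OMM (FT-OMM) and their mothers". The donor-milk group (Group B) is also 25.

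Neither section gives a mean, an SD, a coefficient of variation, a correlation between repeated measurements, a dropout allowance or a power command.

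**The concern.** Group size, significance level, sidedness and an effect in SD units are all stated, so the power can be recomputed, and 95% is far out of reach. A difference of a tenth of an SD is very small, and 25 per group is a small sample.

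The protocol's own Study I calculation (section 2.3.5.1) shows the mismatch. It uses 40 per group to detect 0.75 SD with at least 90% power. Study II claims more power, for an effect 7.5 times smaller (0.75 / 0.10), with 15 fewer participants per group.

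What is at stake is how the results are read. Someone relying on section 3.3.5 would take a non-significant between-group result on growth or infections as strong evidence against even trivial differences. The design can rarely detect anything that small, and it reaches 95% power only for differences of about 1 SD.

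**Working it through.** **Inputs**

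- n = 25 per group (sections 3.3.1 and 3.3.5)
- two-sided α = 0.05 (section 3.3.5)
- d = 0.10, which is what a 10% standardized mean difference means: the difference in means divided by the SD (section 3.3.5)
- claimed power: at least 0.95 (section 3.3.5)

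**Step 1. Try to reproduce the stated figure.** For two equal groups the noncentrality parameter is d × √(n/2) = 0.10 × √12.5 = 0.354. The critical value of t with 48 degrees of freedom is 2.011.

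- Exact noncentral t, both tails: power = 0.064.
- Normal approximation, upper tail: Φ(0.354 − 1.960) = Φ(−1.606) = 0.054.

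The stated 95% is not reproduced.

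**Step 2. Sample size that 95% power would need.** n per group = 2 × (1.960 + 1.645)² / 0.10² = 2,599 by the normal approximation, and 2,600 by exact t. That is 2,600 / 25 = 104 times the planned group size.

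**Step 3. What 25 per group delivers.** Solving the exact power equation for d:

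| Power | Detectable difference |
|---|---|
| 80% | 0.81 SD |
| 90% | 0.94 SD |
| 95% | 1.04 SD |

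**Step 4. Check the method on Study I.** With 40 per group and d = 0.75, the same exact formula gives 91%, in line with the at least 90% in section 2.3.5.1.

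**Step 5. Other readings with the effect kept at 0.10.**

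| Reading | Power |
|---|---|
| One-sided test, 25 vs 25 | 9.7% |
| 50 preterm vs 25 full-term | 6.9% |
| Paired or one-sample, n = 25 / 50 / 75 | 7.7% / 10.7% / 13.7% |
| Three-group ANOVA, f = 0.10 | 10.8% |
| Mean of six visits, intraclass correlation 0.8 down to 0 | 6.7% to 13.6% |
| Covariate correlated 0.9 / 0.99 with the outcome | 12.5% / 69% |
| Correlation of 0.10, n = 25 to 75 | 6.8% to 13.4% |
| R² of 0.10, n = 75 | 79% |

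None reaches 95%.

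**Step 6. Reading 10% as relative to the mean.** Then d = 0.10 / CV, where CV is the between-subject coefficient of variation. For 95% power, CV must be at most 0.10 / 1.041 = 0.096. The protocol states no CV, so the values below are assumptions:

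| Assumed CV | d = 0.10 / CV | Power, 25 vs 25 |
|---|---|---|
| 10% | 1.00 | 93% |
| 15% | 0.67 | 64% |
| 20% | 0.50 | 41% |
| 30% | 0.33 | 21% |

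For disease counts this reading is hard to sustain. If a count followed a Poisson distribution, its CV would be 1/√mean, so a CV below 10% would need a mean above 100 episodes per infant.

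**The case against.** The best defence is that the phrase is ambiguous. Where the protocol means SD units, in Study I, it says so and prints the command. A percentage with neither an SD nor a command may have been meant as a 10% relative difference, and with a low enough CV the claim could then be true for some outcomes. On that reading the 95% is unsupported rather than shown to be false. This deserves to be said, and it is why the 6.4% is tied to the text as written. But it sets aside the word standardized, and one CV of about 9.6% or less would have to hold for milk fat, milk protein, growth and disease counts alike. Nothing in the protocol supports that. A slip from 1.0 SD to 10% is also conceivable, but 1.0 SD gives 93%, still short of 95%.

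Three further points limit the consequence without removing the error:

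- Section 3.3.6 plans regressions of growth and disease counts on milk composition, and a before-and-after pasteurization comparison. It names no direct test of donor milk against own mother's milk on growth or infections. The misread null result is therefore an inference from section 3.3.5, which frames the power as mean differences. Figure 3.2, on group comparisons, is not available to settle it.
- Differences below 1 SD are not invisible. An observed difference of about 0.57 SD (2.011 × √(2/25)) would reach significance, and a true 0.81 SD has 80% power.
- Study II is observational, and the protocol nowhere claims equivalence. Even so, this sentence is the only justification offered for 75 dyads.

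**Conclusion.** The concern holds. On the protocol's own inputs, power for a 10% standardized difference is 6.4%, against at least 95% stated. The planned group is about one hundredth of the size that claim would need. With 25 per group the design has 80% power for 0.81 SD and 95% power for 1.04 SD.

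These figures assume an unadjusted comparison of two groups with a common SD, approximately normal outcomes and all 25 per group evaluable. Losses over the six months would lower the power. Disease counts and the batch-level pasteurization comparison would need their own calculations. The relative-difference reading rescues the claim only at a CV of about 9.6% or less, which the protocol does not state for any outcome. The sentence has to be corrected because the whole sample-size rationale rests on it.

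**What to change.** Keep 25 per group, delete the 10% claim in section 3.3.5 and replace it with wording such as:

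> With 25 dyads per group and complete data, an unadjusted two-group comparison at the two-sided 5% level has 80% power for a difference of 0.81 SD and 95% power for 1.04 SD.

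If a relative difference was intended, say so, and give the mean and SD used for each outcome with the resulting power.

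In either case, add that non-significant comparisons of growth or infections do not show that the groups are equivalent.

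The cost is one reworded paragraph and a less favourable stated detectable effect. No participants, visits or measurements are added.

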3.2. Objectives

The objectives of the study are:

- a) to evaluate associations between the mother's diet composition and HM composition in pre- and full-term infants, i.e. how the potential associations between mother's diet and HM nutrient composition is affected by prematurity.
- b) to evaluate the effect of pasteurization/storage on DHM composition.

c) to evaluate associations between HM composition (OMM or DHM) on growth and other health parameters in pre- and full-term infants.

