3.3.6. Statistical analysis

Associations between mothers' diet and HM composition will be examined with linear regression models. Associations with the macro- and micro-nutrients of the mothers' diet as the independent variable and HM macro- and micro-nutrient composition as dependent variable using prematurity, age and years of education as covariates, will also be examined using linear regression models. The analyses will be repeated separately from the groups of PT-OMM and FT-OMM. Furthermore, linear regression models will be performed with the HM macro- and micro-nutrient composition as the independent

variables and weight, length, cranial perimeter and number of diseases as the dependent using prematurity, age, years of education etc., as the covariates. The analyses will be repeated separately for the groups of preterm and full-term infants. Finally, composition of DHM in terms of nutrients and microorganisms content will be compared before and after pasteurization/storage using Student's t-test or Mann-Whitney test. The analyses will be performed by using STATA software (STATA Corp LLL, College Station, TX, USA).

Finally, additional statistical analysis with the view of deriving additional insights and influences in personalised nutrition will be presented in D2.5.

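### Study II is sized for mean differences, but its analysis section names no comparison of means between the three study groups

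*Protocol*

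**What the plan says.** Section 3.3.5 (Study II) sets its target as "evaluation of 10% standardized mean differences of fat and protein composition of HM, as well as growth markers (weight, height), and health status", with growth and health taken in preterm infants. The power claimed is at least 95% with a two-sided test at the 5% level, and the section concludes that "a total of 75 mother-infant dyads (25 per Group of Study II) will be enrolled". It gives no SD, no coefficient of variation and no regression effect size, and does not say which groups are compared.

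Section 3.3.1 defines the groups: 25 PT-OMM, 25 PT-DHM and 25 FT-OMM dyads, not randomized.

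Section 3.3.6 plans three things:

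- Linear regressions of milk composition on maternal diet, adjusted for prematurity, age and education. Then: "The analyses will be repeated separately from the groups of PT-OMM and FT-OMM".
- Linear regressions of weight, length, cranial perimeter and number of diseases on milk composition, with the same covariates and an open-ended *etc.* Then: "The analyses will be repeated separately for the groups of preterm and full-term infants".
- A Student's t-test or Mann-Whitney test of donor milk composition before versus after pasteurization and storage.

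Section 3.2 frames objective (a) as "to evaluate associations between the mother's diet composition and HM composition in pre- and full-term infants". Objective (b) is the effect of pasteurization and storage. Objective (c) is the association of milk composition, own mother's or donor, with growth and health.

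**The concern.** The two sections describe different analyses. A power statement for a difference in means in preterm infants points to PT-OMM versus PT-DHM, because those are the only preterm groups. Section 3.1 motivates the study partly by the scarcity of reports comparing donor milk with own mother's milk, and by inconclusive evidence of slower growth on donor milk. Yet section 3.3.6 never names milk type as a term, and its preterm growth model pools 50 infants fed two kinds of milk.

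Two things are at stake. The contrast that the sample size implies could go unestimated, or be added after the data are seen. And a reader could take the 95% as the sensitivity of the slopes that are reported, so that a null slope from 25 dyads is read as no association.

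**Working it through.** **1. The plan's own figure.** Inputs from section 3.3.5: two-sided 5%, 25 per group, difference 0.10 SD (10% standardized, read literally). For a two-sample t-test the noncentrality is d × √(n/2) = 0.10 × √12.5 = 0.354, with 48 degrees of freedom. Power is 6.4% (5.4% by the normal approximation), not 95%. Reaching 95% at 0.10 SD would take 2,599 per group.

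**2. What 25 versus 25 detects.** Solving the same formula for d gives 1.04 SD at 95% power and 0.81 SD at 80%. If the 10% means 10% of the mean, 95% power requires a coefficient of variation of at most 0.10/1.04 = 9.6%. The protocol gives none; assuming 15% or 20% instead, power is 64% or 41%.

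**3. Planned analyses against the sized contrast.**

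| Analysis in 3.3.6 | Dyads | Compares means between dyad groups? |
|---|---|---|
| Milk on diet, pooled | up to 75 (50 if own-milk dyads only) | No; prematurity is a covariate |
| Milk on diet, PT-OMM | 25 | No |
| Milk on diet, FT-OMM | 25 | No |
| Growth or illness on milk, pooled | up to 75 | No; prematurity is a covariate |
| Growth or illness on milk, preterm | 50 | No; milk type not named |
| Growth or illness on milk, full-term | 25 | No |
| Donor milk before vs after processing | batches, number not stated | No; compares milk samples |

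Three of the six regression fits rest on 25 dyads.

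**4. What the regressions can detect.** Test one coefficient with partial correlation r, N dyads and k covariates, assuming one observation per dyad. Noncentral F: noncentrality N r²/(1 − r²) on 1 and N − k − 2 degrees of freedom. Fisher z: atanh(r) × √(N − k − 3). Ranges run from F to Fisher z, with k = 0 to 2 at N = 25 and k = 0 to 3 at N = 50.

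| N | r at 80% power | r at 95% power |
|---|---|---|
| 25 | 0.51-0.56 | 0.60-0.67 |
| 50 | 0.38-0.40 | 0.46-0.50 |

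**5. Does moving from means to slopes lose power?** Convert with r = d/√(d² + 4), for equal groups.

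- d = 1.04 gives r = 1.04/√(1.08 + 4) = 0.46. Power is about 70% by F (61-65% by Fisher z) at N = 25, about 95% by F (91-93% by Fisher z) at N = 50, and about 99% at N = 75.
- d = 0.10 gives r = 0.10/√4.01 = 0.05. Power at N = 50 is 6.4%, the same as the 25-versus-25 comparison in step 1.

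The shortfall against an equivalent mean comparison is therefore specific to the fits of 25.

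**The case against.** The strongest defence is that the regressions match the objectives, which are associations plus the pasteurization question, and that section 3.3.5 makes no power claim for them. Figure 3.2, whose title announces group comparisons by objective, is not shown. The growth-model covariates end in *etc.*, and further analysis is deferred to D2.5. The pooled diet model also yields an adjusted preterm versus full-term difference in milk composition through its prematurity term.

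Much of this stands, and it rules out three stronger readings that a reader might infer:

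- *That only regressions are planned.* The donor milk test is a test of means on milk composition. It does not, however, compare dyad groups, and it has no bearing on infant growth or illness.
- *That the regressions all fall short of a promised 95%.* None was promised for them, and at r = 0.46 the fits of 50 and 75 reach about that level.
- *That PT-OMM versus PT-DHM will never be estimated.* The unseen figure and the open covariate list do not allow that. What can be said is that the contrast is not specified.

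The defence does not remove the mismatch. Section 3.3.5 states a mean-difference criterion for preterm infants, and section 3.3.6 contains no test that matches it, whatever Figure 3.2 depicts. The prematurity term cannot separate PT-OMM from PT-DHM, since both are preterm. Because the conflict lies between two written sections, it is not a detail left to a later analysis plan.

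**Conclusion.** The point holds as a mismatch between sections 3.3.5 and 3.3.6. The sample size rests on standardized mean differences, while no comparison of means between PT-OMM, PT-DHM and FT-OMM is named. The implied PT-OMM versus PT-DHM contrast in growth and illness is unspecified, and the stated power describes none of the regressions.

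The 95% is also wrong for the mean comparison itself on the literal reading (about 6%), so it must be recalculated and not simply moved to a newly added test.

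This rests on three assumptions: *standardized* means in SD units, each dyad contributes one observation, and no dyads are lost. That the growth and illness criterion means PT-OMM versus PT-DHM is an inference from the group definitions; the protocol does not say so.

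**What to change.** Keep 75 dyads and make the two sections describe the same analyses.

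1. In 3.3.6, add adjusted mean differences with 95% confidence intervals: PT-OMM versus PT-DHM for infant growth and number of illnesses, and PT-OMM versus FT-OMM for milk fat and protein. Fit the milk-type contrast as its own model. Placed inside the composition models, it would remove between-type variation that is part of the exposure under objective (c).
2. In 3.3.5, attach power only to these comparisons and restate it: 25 versus 25 gives 95% power at about 1.04 SD and 80% at about 0.81 SD.
3. For the regressions, state the partial correlation detectable with 80% power (about 0.51-0.56 with 25 dyads, 0.38-0.40 with 50), and label the single-group fits of 25 as exploratory.

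The cost is protocol wording and a few added models on data already being collected, with no extra participants or measurements. The stated sensitivity becomes less favourable.

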3.3.6. Statistical analysis

Associations between mothers' diet and HM composition will be examined with linear regression models. Associations with the macro- and micro-nutrients of the mothers' diet as the independent variable and HM macro- and micro-nutrient composition as dependent variable using prematurity, age and years of education as covariates, will also be examined using linear regression models. The analyses will be repeated separately from the groups of PT-OMM and FT-OMM. Furthermore, linear regression models will be performed with the HM macro- and micro-nutrient composition as the independent

variables and weight, length, cranial perimeter and number of diseases as the dependent using prematurity, age, years of education etc., as the covariates. The analyses will be repeated separately for the groups of preterm and full-term infants. Finally, composition of DHM in terms of nutrients and microorganisms content will be compared before and after pasteurization/storage using Student's t-test or Mann-Whitney test. The analyses will be performed by using STATA software (STATA Corp LLL, College Station, TX, USA).

Finally, additional statistical analysis with the view of deriving additional insights and influences in personalised nutrition will be presented in D2.5.

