3.3.4.1. Measurements

Measurements concern sociodemographic information, dietary and other lifestyle behaviors, anthropometry, medical history, genotype, metabolome, and microbiome.

Dietary assessment

Upon every visit of the observational phase mothers of PT-OMM, PT-DHM, and FT-OMM as well as donors providing the DHM will complete a validated semi-quantitative food frequency questionnaire (FFQ) [35], from which MedDietScore, will be calculated [36], as described in section 3.3.3.

In addition, during the hospital visit at month 1 all mothers will be asked to return a 4-day food record, in which they will have recorded all foods and drinks consumed for three consecutive weekdays and one day of the weekend. Nutrients' intake will be calculated using the Nutritionist Pro™ Diet Analysis (Axxya Systems, Woodinville, WA, USA) software. The research team involved in the diet analysis is competent in using the proposed software, and HUA has a long history of analyzing dietary data through it. Another strength of the proposed software is that it comprises food databases from multiple countries, which can be used to extrapolate the most relevant and reliable reference. We aim to cross-match intake data, and compare the validity of the FFQ against the 4-day food record, in order for the most valid to be used in the platform.

Other lifestyle behaviors assessment

Physical activity levels of mothers of PT-OMM, FT-OMM and PT-OMM as well as milk donors providing DHM will be evaluated at every visit, as described in section 3.3.3.

Furthermore, the mothers will be asked regarding their smoking habits [38]. In specific current smoking status (yes/no), smoking frequency (1, daily; 2, less than daily; 3, not at all) and exposure to second hand smoking (yes/no) will be recorded.

[figure not shown]
Anthropometric assessment

Weight and height of mothers of the PT-OMM, PT-DHM, and FT-OMM, as well as milk donors providing DHM will be measured and recorded at every visit at the hospital, as described above.

All infants will be evaluated regarding their growth by measuring weight, length and cranial perimeter upon every visit at the hospital. Weight and recumbent length will be measured on an electronic baby scale and on a neonatometer scale, to the nearest 0.5 kg and 0.5 cm respectively and cranial perimeter will be measured using a flexible inch tape to the nearest 0.5 cm.

Medical history assessment

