Number of respiratory, gastrointestinal, and neurologic infections, number of hospital admissions due to infectious diseases as well as antibiotics use will be recorded for infants of all three groups upon every visit.

o Metabolome characterisation

For the characterization of metabolic profile urine samples will be collected from mothers of PT-OMM, PT-DHM and FT-OMM and their infants at each evaluation, as described in Deliverables 2.2 and 3.1.

Human milk nutrient composition assessment

OMM will be collected at every visit. DHM aliquots of each milk batch will be collected before and after pasteurization and fortification of DHM will be recorded. The detailed protocol is described in Deliverable 2.3.

Microbiome assessment

OMM and DHM before pasteurization will be analyzed for microorganism's content. Fecal samples from mothers of PT-OMM, PT-DHM and FT-OMM and their infants will be also collected for studying the microbiome at every visit. The protocol followed is described in Deliverable 2.1.

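### Study II, objective (a): the plan neither estimates nor tests whether the diet–milk slope differs between preterm and full-term dyads

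*Protocol*

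**What the plan says.** Objective (a) in Protocol section 3.2 has two halves. The first is to evaluate diet–milk associations in preterm and full-term infants. The second explains this as "how the potential associations between mother's diet and HM nutrient composition is affected by prematurity", which is a question of effect modification.

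Section 3.3.6 gives the analysis. Milk nutrients are regressed on maternal diet nutrients by linear regression, with prematurity, age and years of education as covariates. Then "The analyses will be repeated separately from the groups of PT-OMM and FT-OMM". No product term and no comparison of slopes is named. Further work is deferred to deliverable D2.5, described only as additional insights for personalised nutrition.

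On data collection, section 3.3.4.1 states that "OMM will be collected at every visit". It has the food frequency questionnaire (FFQ) completed "Upon every visit of the observational phase mothers of PT-OMM, PT-DHM, and FT-OMM". Section 3.3.2 lists visits at baseline, at complete enteral nutrition (preterm) or recovery of birth weight (full term), and at months 1, 2, 3 and 6. Section 3.3.6 does not say which visit or summary enters the regression.

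**The concern.** A regression with prematurity as a plain covariate lets the level of a milk nutrient differ between groups but forces the diet slope to be equal. It assumes away what objective (a) asks about. The separate fits release that constraint, but they give two estimates, each tested against zero, and neither is compared with the other.

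Someone writing up the study would then be drawn to set one result beside the other: a nutrient significant in one group and not in the other looks like an effect of prematurity. With 25 dyads per group this pattern is common when the slopes are identical, and section 3.3.6 runs over many macro- and micronutrients. Section 3.4 says the associations will feed the platform and train its algorithm, so a false preterm/full-term contrast would be carried forward.

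**Working it through.** **The plan's own figure.** Section 3.3.5 states "a total of 75 mother-infant dyads (25 per Group of Study II) will be enrolled", with "statistical power of at least 95" per cent, "at 5% significance level of two-sided hypotheses", for "10% standardized mean differences of fat and protein composition of HM". This concerns mean differences; no figure is given for a slope difference. Nor does it reproduce. For d = 0.10 and 25 per group, power is 0.054 (normal approximation, upper tail) or 0.064 (noncentral t), and 95% power needs 2 × (1.960 + 1.645)² / 0.10² ≈ 2,599 per group. That is a separate matter, but it means section 3.3.5 gives no assurance for objective (a).

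**Reading two separate fits against each other.** With equal true slopes and per-group power p, the chance that exactly one group is significant is 2p(1 − p):
- p = 0.32: 2 × 0.32 × 0.68 = 0.44
- p = 0.52: 2 × 0.52 × 0.48 = 0.50, practically the maximum
- p = 0.80: 2 × 0.80 × 0.20 = 0.32
- no association at all (p = 0.05): 2 × 0.05 × 0.95 = 0.095

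Simulation of 25 versus 25 dyads, one value per mother, same true correlation in both groups (assumed), 6,000 replicates:

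| Common correlation | Exactly one group significant | Interaction test rejects |
|---|---|---|
| 0.2 | 27% | 4.9% |
| 0.3 | 43% | 5.2% |
| 0.4 | 50% | 5.1% |
| 0.5 | 38% | 5.4% |

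**What an interaction term can detect.** In units of residual SD per SD of diet, the standard error of the slope difference is about √(1/25 + 1/25) = 0.283 (normal approximation, one value per mother, no dropout).
- 80% power: (1.960 + 0.842) × 0.283 ≈ 0.79
- 95% power: (1.960 + 1.645) × 0.283 ≈ 1.02
- Power for differences of 0.1, 0.3, 0.5 and 0.8: 6%, 19%, 42% and 81%
- 95% CI half-width: 1.96 × 0.283 ≈ 0.55

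For scale, if one slope is zero, a slope of 0.79 in the other group corresponds to a correlation of 0.79 / √(1 + 0.79²) ≈ 0.62.

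**Only if several visits per mother enter as independent rows.** The variance of the slope is understated by 1 + (m − 1) × ρ_diet × ρ_milk, where m is the number of visits and ρ the within-mother correlations. The documents give no correlations; those below are assumptions. Actual error of a nominal 5% test with m = 6:
- ρ_diet = 0: factor 1.0, error 5%
- both 0.3: factor 1.45, error 10%
- both 0.7: factor 3.45, error 29%
- diet constant within mother (1.0), ρ_milk = 0.7: factor 4.5, error 36%

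Simulation with 50 mothers agrees (5%, 10%, 29%, 36%). With m = 5 the last three become 9%, 26% and 32%.

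**The case against.** The separate regressions answer the first half of objective (a) directly, and anyone holding both slopes and standard errors can form the difference by hand. That stands: the objective is described, and what is missing is the comparison. A statistical analysis plan may exist, and Figure 3.2, which maps group comparisons to objectives, is not legible in the text. But section 3.3.6 is not silent on the point. It fixes prematurity as a covariate and names the stratified fits, and D2.5 is reserved for additional work.

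An interaction test at 25 versus 25 is weak, so a non-significant result would say little. True, and the reason to report an interval and state the precision; it does not justify inferring a difference from two separate tests.

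Two stronger readings are tempting and not supported. One is that the plan will declare a difference whenever one group is significant and the other is not. No such rule is written, so the 27% to 50% measures the risk of that reading and is not an error rate of the plan.

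The other is that p-values will be too small because ordinary regression is run on all visits. Section 3.3.6 never says visits enter as independent rows. In Study II, nutrient calculation is described only for the 4-day food record, returned once at month 1; the repeated FFQ is described as the source of the MedDietScore. A month-1 or per-mother-mean analysis has no clustering problem. Likewise, months 1, 2, 3 and 6 are common to both groups, and only the enteral-nutrition or birth-weight visit is anchored differently.

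**Conclusion.** The point holds for the second half of objective (a): as written, section 3.3.6 neither estimates nor tests how the diet–milk slope differs with prematurity. The size of the risk depends on the common correlation, which is assumed. It is 27% to 50% for 0.2 to 0.5, about 10% where diet and milk are unrelated, and it falls again when the association is strong enough to be found in both groups. The interaction test stays near 5% across the correlations simulated.

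The repeated-visit issue stands only as a condition. If more than one visit per mother is used without allowing for correlation, a nominal 5% test has an actual error of about 5% to 36% over the assumed range. The lower end applies when diet is uncorrelated within mothers.

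**What to change.** In section 3.3.6, for objective (a), fit one linear model to PT-OMM and FT-OMM together with the diet nutrient, prematurity, their product and the existing covariates, stating whether age is maternal or infant. Answer the objective by the slope difference with its 95% confidence interval, and keep the group-specific slopes as description. Add a sentence that 25 versus 25 has about 80% power only for a difference of about 0.8 residual SD per SD of diet, so a non-significant interaction is not evidence of equal slopes.

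State which visit or per-mother summary is analysed. If more than one visit per mother enters, add a random intercept per mother or cluster-robust standard errors, and days postpartum at sampling. The Protocol's own background (section 3.1) says that early preterm milk differs in protein and fat from milk of later lactation.

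In the growth models the repeated unit is the infant, since PT-DHM milk comes from donors; any clustering term belongs there. Number of diseases is a count and needs a count model rather than linear regression.

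The cost is a few sentences and standard models in the software already named. No new data or participants are needed.
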